11.2.8 Abscopal response rate

Abscopal response is defined as described previously [62] to be a decrease in the longest diameter of at least 30% in any measurable (>1cm) non-irradiated lesion from baseline. A complete abscopal response is defined as the complete disappearance of a measurable non-irradiated lesion and a partial abscopal response was defined as at least a 3-% decrease in the longest diameter. Progressive disease in this context is defined as at least a 20% increase in the longest diameter of the best measurable non-irradiated lesion, whereas stable disease was defined as insufficient shrinkage or growth to qualify for a partial abscopal response or complete abscopal response or progressive disease.

12. DATA REPORTING / REGULATORY REQUIREMENTS

Adverse event lists, guidelines, and instructions for AE reporting can be found in Section 7.0 (Adverse Events: List and Reporting Requirements).

12.1 Data Reporting

12.1.1 Method

The ODQ will collect, manage, and perform quality checks on the data for this study.

12.1.2 Responsibility for Data Submission

Investigative sites within DF/HCC or DF/PCC are responsible for submitting data and/or data forms to the ODQ according to the schedule set by the ODQ.

12.2 Data Safety Monitoring

The DF/HCC Data and Safety Monitoring Committee (DSMC) will review and monitor toxicity and accrual data from this study. The committee is composed of clinical specialists with experience in oncology and who have no direct relationship with the study. Information that raises any questions about participant safety will be addressed with the Overall PI and study team.

The DSMC will review each protocol up to four times a year or more often if required to review toxicity and accrual data. Information to be provided to the committee may include: up-to-date participant accrual; current dose level information; DLT information; all grade 2 or higher unexpected adverse events that have been reported; summary of all deaths occurring with 30 days of intervention for Phase I or II protocols; for gene therapy protocols, summary of all deaths while being treated and during active follow-up; any response information; audit results, and a summary

provided by the study team. Other information (e.g. scans, laboratory values) will be provided upon request.

12.3 Multi-Center Guidelines

This protocol will adhere to DF/HCC Policy MULTI-100 and the requirements of the DF/HCC Multi-Center Data and Safety Monitoring Plan. The specific responsibilities of the Sponsor-Investigator, Coordinating Center, and Participating Institutions and the procedures for auditing are presented in Appendix J.

13. STATISTICAL CONSIDERATIONS

13.1 Study Design/Endpoints

This phase 2 study will enroll patients who have previously progressed on PD-1 directed therapy, for whom response to pembrolizumab monotherapy is unlikely. These patients usually progress rapidly within a span of a few months and the expected progression-free survival rate at 3 months is about 35%. Therefore, the combined treatment will be considered promising and worthy of further evaluation if there is evidence that the 3-month progression-free survival (PFS) is approximately 65%. A two-stage design will be employed and a safety run-in phase will be conducted using a 3+3 design.

Safety Run-In:

The safety run-in phase will follow a 3+3 design. Initially 3 patients will be entered. If none of the 3 patients experiences dose-limiting toxicity (DLT), the safety run-in phase will end and the study will proceed. If 1 out of 3 patients experiences a DLT, an additional 3 patients will be entered. If none of the additional 3 patients experiences a DLT, the study will proceed. If at any time 2 (or more) patients experience a DLT in the run-in phase, the study will be terminated. Treatment safety will continue to be monitored after the run-in phase. If there are 33% or more of patients with a DLT at any time during the phase II portion, the study will pause and a detailed safety analysis will be conducted.

Phase II:

A two-stage design will be used in the phase II portion of this study. The first stage will accrue 6 patients and the patients in the run-in phase will be included in the stage I accrual. If at least 2 patients are progression-free and alive at 3 months, an additional 13 patients will be entered. If 10 or more patients are progression-free and alive at 3 months among 19 patients, the combination treatment will be considered worthy of further study for this group of patients. With this design, we will have 90% power to test the PFS rate of 65% vs. 35% based on a 0.08 level one-sided test.

If only 0 or 1 patient is progression-free at 3 months among the 6 patients in stage I accrual, the same design (safety run-in plus two-stage design) will be used to examine the combination treatment of pembrolizumab plus hypofractionated and low dose radiation (cohort B).

CONFIDENTIAL

This document is confidential. Do not disclose or use except as authorized.

13.2 Sample Size, Accrual Rate and Study Duration

We plan to accrue 20 patients for a cohort in the phase II portion to allow for 1 unevaluable patient. The maximum sample size will be 26 patients if the enrollment to cohort B starts. The expected accrual rate is 1-2 patients per month, and the accrual of 26 patients is expected to complete in 18 months.

13.3 Stratification Factors

Patients will not be stratified; however, analyses will be performed on patients with HPV-associated and non-HPV associated disease.

13.4 Analysis of Primary Endpoint

The primary endpoint of this study is PFS rate at 3 months. Proportion of patients progression-free and alive at 3 months will be reported and the method of Atkinson and Brown will be used to compute the confidence interval of PFS rate for the cohort that has two stages of accrual. The Kaplan-Meier method will also be used to characterize PFS and PFS is defined as the time from registration to disease progression or death, whichever occurs first. Patients who are alive and progression-free will be censored at the date of last disease assessment.

13.5 Analysis of Secondary Endpoints

Efficacy Endpoints

The secondary endpoints of this study include local response within the irradiated fields, overall response per RECIST 1.1 and irRC, abscopal response and overall survival. Various types of response rates will be reported along with 90% exact binomial confidence intervals. The Kaplan-Meier method will be used to characterize overall survival.

Safety and tolerability

All patients will be evaluable for toxicity from the time of their first treatment with any study agent. Toxicity will be graded according to NCI CTCAE, Version 4.0 and summarized by maximum grade. Incidence rate of each toxicity will be reported with 90% exact binomial confidence intervals. Number of patients with DLTs will also be reported.

Correlative endpoints

Analyses of correlative endpoints are largely exploratory and hypothesis-generating and will be descriptive in nature. Any promising findings will be tested in future studies. Assuming 16 patients have baseline and post cycle 2 biospecimen available for analyses of tumor infiltrating lymphocytes (expressed as a percentage) and also for PD-L1 and PD-L2 expression (expressed as H-scores and also as percent positive), the study will have 80% power to detect a 0.65 SD change

CONFIDENTIAL

This document is confidential. Do not disclose or use except as authorized.

in mean of a quantitative correlative parameter using Wilcoxon signed rank test with two-sided type I error of 0.1.

13.6 Reporting and Exclusions

Evaluation of Efficacy

For this Phase II trial, the efficacy evaluable population will be eligible patients who receive protocol therapy.

Evaluation of Safety

The safety population will be used in the safety data summaries. The safety population consists of all patients who took at least one dose of any protocol therapy and who have at least one post-baseline safety assessment. Note that a patient who had no adverse events constitutes a safety assessment. Patients who have received at least one dose of study drug but have no post-treatment safety data of any kind would be excluded.

14. PUBLICATION PLAN

The results should be made public within 24 months of reaching the end of the study. The end of the study is the time point at which the last data items are to be reported, or after the outcome data are sufficiently mature for analysis, as defined in the section on Sample Size, Accrual Rate and Study Duration. If a report is planned to be published in a peer-reviewed journal, then that initial release may be an abstract that meets the requirements of the International Committee of Medical Journal Editors. A full report of the outcomes should be made public no later than three (3) years after the end of the study.

16. APPENDICES

Appendix A: Performance Status Criteria

ECOG Performance Status Scale		Karnofsky Performance Scale	
Grade	Description	Percent	Description
0	Normal activity. Fully active, able to carry on all pre-disease performance without restriction.	100	Normal, no complaints, no evidence of disease.
		90	Able to carry on normal activity; minor signs or symptoms of disease.
1	Symptoms, but ambulatory. Restricted in physically strenuous activity, but ambulatory and able to carry out work of a light or sedentary nature (e.g., light housework, office work).	80	Normal activity with effort; some signs or symptoms of disease.
		70	Cares for self, unable to carry on normal activity or to do active work.
2	In bed < 50% of the time. Ambulatory and capable of all self-care, but unable to carry out any work activities. Up and about more than 50% of waking hours.	60	Requires occasional assistance, but is able to care for most of his/her needs.
		50	Requires considerable assistance and frequent medical care.
3	In bed >50% of the time. Capable of only limited self-care, confined to bed or chair more than 50% of waking hours.	40	Disabled, requires special care and assistance.
		30	Severely disabled, hospitalization indicated. Death not imminent.
4	100% bedridden. Completely disabled. Cannot carry on any self-care. Totally confined to bed or chair.	20	Very sick, hospitalization indicated. Death not imminent.
		10	Moribund, fatal processes progressing rapidly.
5	Dead.	0	Dead.

CONFIDENTIAL

This document is confidential. Do not disclose or use except as authorized.

APPENDIX B: Pembrolizumab Events of Clinical Interest

Pneumonitis (reported as ECI if ≥ Grade 2)		
Acute interstitial pneumonitis	Interstitial lung disease	Pneumonitis
Colitis (reported as ECI if ≥ Grade 2 or any grade resulting in dose modification or use of systemic steroids to treat the AE)		
Intestinal Obstruction	Colitis	Colitis microscopic
Enterocolitis	Enterocolitis hemorrhagic	Gastrointestinal perforation
Necrotizing colitis	Diarrhea	
Endocrine (reported as ECI if ≥ Grade 3 or ≥ Grade 2 and resulting in dose modification or use of systemic steroids to treat the AE)		
Adrenal Insufficiency	Hyperthyroidism	Hypophysitis
Hypopituitarism	Hypothyroidism	Thyroid disorder
Thyroiditis	Hyperglycemia, if ≥Grade 3 and associated with ketosis or metabolic acidosis (DKA)	
Endocrine (reported as ECI)		
Type 1 diabetes mellitus (if new onset)		
Hematologic (reported as ECI if ≥ Grade 3 or any grade resulting in dose modification or use of systemic steroids to treat the AE)		
Autoimmune hemolytic anemia	Aplastic anemia	Thrombotic Thrombocytopenic Purpura (TTP)
Idiopathic (or immune) Thrombocytopenia Purpura (ITP)	Disseminated Intravascular Coagulation (DIC)	Haemolytic Uraemic Syndrome (HUS)
Any Grade 4 anemia regardless of underlying mechanism		
Hepatic (reported as ECI if ≥ Grade 2, or any grade resulting in dose modification or use of systemic steroids to treat the AE)		
Hepatitis	Autoimmune hepatitis	Transaminase elevations (ALT and/or AST)
Infusion Reactions (reported as ECI for any grade)		
Allergic reaction	Anaphylaxis	Cytokine release syndrome
Serum sickness	Infusion reactions	Infusion-like reactions
Neurologic (reported as ECI for any grade)		
Autoimmune neuropathy	Guillain-Barre syndrome	Demyelinating polyneuropathy
Myasthenic syndrome		
Ocular (report as ECI if ≥ Grade 2 or any grade resulting in dose modification or use of systemic steroids to treat the AE)		
Uveitis	Iritis	
Renal (reported as ECI if ≥ Grade 2)		
Nephritis	Nephritis autoimmune	Renal Failure
Renal failure acute	Creatinine elevations (report as ECI if ≥Grade 3 or any grade resulting in dose modification or use of systemic steroids to treat the AE)	
Skin (reported as ECI for any grade)		
Dermatitis exfoliative	Erythema multiforme	Stevens-Johnson syndrome
Toxic epidermal necrolysis		
Skin (reported as ECI if ≥ Grade 3)		
Pruritus	Rash	Rash generalized
Rash maculo-papular		
Any rash considered clinically significant in the physician's judgment		
Other (reported as ECI for any grade)		
Myocarditis	Pancreatitis	Pericarditis
Any other Grade 3 event which is considered immune-related by the physician		

CONFIDENTIAL

This document is confidential. Do not disclose or use except as authorized.

APPENDIX C: Guidelines for collecting research biopsy tissue

Tissue specimens will be collected from metastatic lesions using standard institutional procedures. The amount of tissue collected may follow the guidelines listed below:

*Skin/*chest wall: A goal of 2 5-mm punch biopsies will be obtained.

Lymph node: A goal of 3-6 core biopsy specimens will be obtained using an 18-gauge needle.

Liver: A goal of 3-6 core biopsy specimens will be obtained using an 18-gauge needle.

Lung: Because of the risk of pneumothorax associated with core needle biopsies of lung nodules, no core biopsies of lung nodules are mandated on this protocol, unless they are clinically indicated.

Bone: Because the yield of malignant tissue from bone biopsies tends to be relatively low, if a patient has another accessible site of disease (i.e. skin, lymph node, liver), that site should be biopsied preferentially. If bone is the only biopsy-accessible site, then a goal of 3-6 core biopsy specimens will be obtained using an 11-13 gauge needle.

Please note that the above are guidelines for the amount of tissue to be obtained, and are not meant to replace clinical judgment at the time the procedure is performed. Less than the goal quantity of tissue is accepted for each type of biopsy, and will be left to the clinical judgment of the physician performing the procedure.

If a patient is undergoing resection of a lesion for clinical reasons (i.e. wedge resection of a new lung lesion for confirmation of diagnosis or re-testing of hormone receptor or HER2 status; or, resection of a chest wall lesion; or, resection of a lymph node), then the patient may opt to have a portion of that tissue (roughly equivalent to the goal amount of tissue listed in the guidelines above, i.e. the equivalent of two 5-mm punch biopsies of the skin, or 3-6 18-gauge core biopsies) stored for research at the time of the procedure (provided that the tissue is processed as specified), in which case, the patient would not be required to undergo a separate research biopsy at baseline on this protocol.

Specimens will be shipped to the Clinical Research Coordinator who will then deliver tissues to pathology:

TBD

Coded laboratory specimens will be stored in the Tumor Bank of the DFCI. These specimens will become the property of DFCI. Patients will be informed that their specimens may be used for research by investigators at DF/HCC and other approved collaborators. Shared specimens will be identified with a sample ID number; all patient identifying material will be removed.

Risks of Research Biopsy and Procedures for Minimizing Risk

CONFIDENTIAL

This document is confidential. Do not disclose or use except as authorized.

Potential risks according to site are:

Skin/cheat wall (punch biopsy):

- Likely: local discomfort and minor bleeding
- Less likely: moderate or major bleeding, or infection

Lymph node, liver, or bone (core needle biopsy):

- Likely: local discomfort and minor bleeding
- Less likely: moderate or major bleeding, need for blood transfusion, hospitalization due to bleeding or other complications, infection, damage to adjacent organs. Additional risks may be present if intravenous conscious sedation is required

Breast (core biopsy):

- Likely: local discomfort and minor bleeding.
- Less likely: moderate or major bleeding, need for blood transfusion, hospitalization due to bleeding or other complications, infection, pneumothorax, damage to adjacent organs.

Pleural fluid (thoracentesis):

- Likely: local discomfort and minor bleeding
- Less likely: moderate or major bleeding, need for blood transfusion, hospitalization due to bleeding or other complications, infection, pneumothorax, damage to adjacent organs

Ascites fluid (paracentesis):

- Likely: local discomfort and minor bleeding
- Less likely: moderate or major bleeding, need for blood transfusion, hospitalization due to bleeding or other complications, infection, bowel perforation or damage to adjacent organs. In order to minimize the risk of a biopsy, only qualified personnel will perform these procedures.

Prior to the procedure, the physician performing the procedure will discuss the risks with each study participant, answer any questions, and obtain separate procedure consent. Patients will be evaluated for comorbidities or concomitant medications that may increase the risk of potential complications. For biopsies of lesions that are not superficial and clearly palpable, imaging studies such as CT or ultrasound will be used to guide the biopsy in order to minimize the risk of damage to adjacent structures. After lymph node biopsies, patients will be observed a minimum of 2 hours (range 2-4 hours) after the procedure, or according to standard institutional guidelines. After liver biopsies, patients will be observed a minimum of 4 hours (range 4-6 hours) after the procedure, or according to standard institutional guidelines. Less than the goal quantity of tissue is accepted for each type of biopsy, and will be left to the clinical judgment of the physician performing the procedure.

Risks of Anesthesia

Local Anesthesia

All biopsy procedures require local anesthesia using lidocaine, xylocaine, or related compounds. There is a small risk of an allergic reaction associated with these drugs. In order to minimize the risk of local anesthesia, only qualified personnel will perform the biopsy procedure. Patients will be queried if they have had previous allergic

reactions to local anesthetics.

Intravenous Conscious Sedation

Certain biopsy procedures, such as lymph node, liver, or bone biopsies, may require intravenous conscious sedation (IVCS). IVCS is a minimally depressed level of consciousness that retains the patient's ability to maintain a patent airway independently and continuously and respond appropriately to physical stimulation and verbal commands.

The risks of intravenous conscious sedation include: inhibition of the gag reflex and concomitant risk of aspiration, cardiopulmonary complications (myocardial infarction, cardiac arrhythmias, hypoxemia), and allergic reactions to the sedative or analgesic medications. These risks are small but real; for example, in a prospective study of 14,149 patients undergoing IVCS during upper gastrointestinal endoscopies, the rate of immediate cardiopulmonary events was 2 in 1000.[63] The 30-day mortality was 1 per 2,000 cases. In this study, there was a strong association between lack of monitoring and use of high-dose benzodiazepines with adverse outcomes. There was also an association between the use of local anesthetic sprays to the oropharynx and the development of pneumonia. In order to minimize the risk of intravenous conscious sedation, only qualified personnel will be responsible for conscious sedation. A minimum of two individuals will be involved in the care of patients undergoing conscious sedation—the physician performing the biopsy procedure, and the individual (M.D. or R.N.) who monitors the patients and his/her response to both the sedation and the procedure, and who is capable of assisting with any supportive or resuscitative measures. The room where the procedure utilizing IVCS takes place will have adequate equipment to provide supplemental oxygen, monitor vital signs, and maintain an airway should this be necessary. An emergency cart will also be immediately accessible to the room where the procedure is to take place, and emergency support services will be available on page. Patients will be screened and evaluated for their fitness to undergo conscious sedation by a trained physician. Patients with active cardiac disease are excluded from this study. No local anesthetic spray to the oropharynx will be necessary, given that endoscopy is not a planned procedure. Following the procedure, patients will be observed closely in the recovery room for a minimum of 2 hours.

General Anesthesia

Because of the higher risk of general anesthesia compared with local anesthesia or intravenous conscious sedation, biopsies that would require general anesthesia in order to be performed *are not permitted* on this protocol, unless they are being done for clinical reasons, and excess tissue that otherwise would have been discarded is then banked for the purpose of this protocol.

CONFIDENTIAL

This document is confidential. Do not disclose or use except as authorized.

For Biopsies of Soft Tissue, Liver, Bone, Breast, Etc:

1. After biopsy is performed, the tissue mass is placed on a sterile gauze
2. Using forceps, separate the tumor tissue
3. Place 2 pieces (cores) of tumor tissue in each cassette (typically end up with 3 cassettes per biopsy); the last cassette will contain many small pieces of tumor tissue
4. Fill cassettes with OCT
 - a. Completely cover tissue
 - b. Limit the amount of bubbles
5. Place cassettes on dry ice and prepare for transport by limiting OCT leakage
6. Return samples to the lab and complete freezing of samples in OCT with dry ice (about 10 minutes freezing time)
7. Once samples are frozen, place in plastic bag; label bag with date, protocol number, patient number, and number of initials included
8. Store in -80C freezer

For Effusions and Ascites

1. Fluid sample should be split into two equal aliquots
2. One aliquot should be spun down into a pellet and snap frozen in an ETOH/dry ice bath or in liquid N2
3. One aliquot should be fixed and processed as a standard cell block.

Note: if the sample preparation is done by a clinical cytopathology laboratory, it is important to explain that the sample is for research purposes only and that no thin prep should be performed as this uses up a significant portion of the sample.

For Fine Needle Aspiration Samples

A goal of 3 passes:

1. One pass should be evacuated and rinsed directly into 2mL of room temperature Trizol for RNA analysis.
2. One pass should be evacuated and rinsed directly into 2mL of room temperature Trizol for DNA analysis.
3. One pass should be evacuated and rinsed directly into 10-20mL of RPMI to prepare a cell block.

Fresh Tissue Shipping Procedures

Please ship frozen specimens over-night on dry ice to the following:

TBD

Please email TBD with the sample information and tracking information the day before shipping a frozen specimen.

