5.3.1 Additional On-Treatment Assessments

Tumor Assessments

Tumor assessments will be performed according to RECIST 1.1 and immune related response criteria (irRC) (see Section 11). Response evaluations will be performed week 5 (+/- 1 week) and then every 8 weeks or as clinically indicated. In case of systemic response, confirmatory scans will be performed 4 weeks after the scan that documented response.

Research Blood Sample Collection

CONFIDENTIAL

This document is confidential. Do not disclose or use except as authorized.

Research blood sample collections should be collected at the following time points:

1. At baseline, within 14 days prior to cycle 1 day 1 of protocol therapy (ideally as close to administration of cycle 1 day 1 therapy as possible)
2. At approximately week 4 (following the completion of all radiation therapy) or cycle 2 of pembrolizumab, then again at week 7 or cycle 3, and at then optionally at later pembrolizumab cycles as applicable.

Specific instructions for research blood draw handling are described in Section 9 and appendices.

Tumor biopsy.

If a tumor is readily accessible, a tumor biopsy is suggested at the following time points:

1. At baseline, ideally as close to administration of cycle 1 day 1 therapy as possible
2. After cycle 2, within 14 days prior to cycle 3 day 1 of protocol therapy and generally after restaging scans to be performed on week 5

Further details about collection and handling of tumor biopsy specimen can be found in Section 9 and appendices.

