9.1.2 Collection, handling and transportation of biopsy specimens

Biopsies should not be performed on Friday afternoons, as there may not be time for processing of the fresh tissue.

If feasible, the protocol will require 2 cores, additional cores (up to 7) will be obtained using an optional consent form.

The order of specimen collection should be:

- First core: 10% neutral buffered formalin
- Second core: Sterile DMEM or RNAlater

Optional cores are alternated between formalin and sterile DMEM/ RNAlater.

After being obtained, processing of the cores is as follows:

- All samples should be de-identified
 - Formalin specimens will be processed into Formalin-fixed paraffin embedded block(s) and or unstained/unbaked slides (15-20), stored at room temperature, as per institutional procedure.
 - Tissue stored in DMEM or RNAlater will be stored at -70 to -80 degrees C.

The study coordinator should be notified before a biopsy specimen is taken / sent to arrange for transfer to the Center for Immuno-Oncology and Core Pathology Laboratories at Dana-Farber Cancer Institute / Brigham and Women's Hospital and to provide most up to date contact and shipping information.

As general guidance , samples should be transported or shipped to:

(DMEM/RNAlater samples):

Center for Immuno-Oncology
Dana-Farber Cancer Institute
[name]
[name]
[contact]

Formalin samples:

Brigham & Women's Hospital
[name]
[name]
[name]

CONFIDENTIAL

This document is confidential. Do not disclose or use except as authorized.

Note: DMEM/RNALater samples should be transported / shipped on dry ice.

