APPENDIX F: Immunohistochemical staining assays

Design of immunohistochemical assay

The immunohistochemical assay for PD-L1 and PD-L2 is semi-quantitative while PD-1 stained slides will be scanned by an automated scanning microscope and quantitatively analyzed by Aperio image analysis system (Lecia Biosystems) after they are evaluated and positive cells are manually counted by a pathologist.

Standard EnVision two-step (indirect) staining method will be utilized. Four micrometer-thick sections will be cut, deparaffinized, rehydrated, and subjected to heat modified antigen retrieval in citrate buffer (pH 6) (Invitrogen) by steaming for 30 minutes. After cooling, tissue sections will be incubated with peroxidase block (DAKO, Carpinteria, CA) for five minutes, then serum free protein block (DAKO) for 20 minutes. Slides will be incubated at room temperature for one hour with a primary antibody. Antibodies will be diluted in Da Vinci Green Diluent (Biocare Medical, Concord, CA). EnVision™ anti-mouse HRP-labeled polymer (DAKO) will be applied to the sections for 30 minutes, followed by visualization using the chromogen 3,3-diaminobenzidine (DAKO). All the sections will then be counterstained with hematoxylin, dehydrated, mounted, and coverslipped. Positive and negative controls shall be included in each staining. Known positive stained Hodgkin Lymphoma (PD-L1), tonsil (PD-1), and melanoma (PD-L2) slides will be used as external control (separate slides). Stained slides will be stored at room temperature.

In a pilot study performed by our correlative scientists, immunoreactivity for PD-L1 was detected in the cytoplasm and membrane while PD-L2 and PD-1 expression was observed in the cytoplasm. Scoring for PD-L1 and PD-L2 will be semi-quantitative/ordered categorical. The percentage of the tumor cells staining positive for PD-L1 or PD-L2 and the intensity of the staining will be recorded (using the scale 0=no staining, 1=weak staining, 2=moderate staining, 3=intense staining). Absolute PD-1 positive cells will be counted under microscope lens x20 power field. Five representative areas will be chosen to count. The average number from 5 areas will be recorded and compared with data from image analysis.

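### Appendix C freezes all fresh core tissue in OCT while Section 9.1.2 sends the first core to formalin; cores handled only by Appendix C cannot enter the paraffin-based PD-L1/PD-L2/PD-1 assay

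*Combined protocol and SAP*

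**What the plan says.** Section 9.1.2 sets the order of collection: "First core: 10% neutral buffered formalin", then "Second core: Sterile DMEM or RNAlater". Any optional cores alternate between those two routes. The fixed material has a stated end product: "Formalin specimens will be processed into Formalin-fixed paraffin embedded block(s) and or unstained/unbaked slides (15-20" in number.

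Appendix C has its own numbered steps for biopsies of soft tissue, liver, bone and similar sites. After the tumor tissue is separated, the steps read "Place 2 pieces (cores) of tumor tissue in each cassette (typically end up with 3 cassettes per biopsy" and "Fill cassettes with OCT", followed by "Return samples to the lab and complete freezing of samples in OCT with dry ice" and storage at -80C. This core route names no formalin, DMEM or RNAlater sample.

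Appendix F describes the immunohistochemistry for PD-L1, PD-L2 and PD-1, which opens with "Four micrometer-thick sections will be cut, deparaffinized, rehydrated".

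On which text applies, Section 5.3.1 says "Further details about collection and handling of tumor biopsy specimen can be found in Section 9 and appendices", and Section 5.2.1 says the same. In the study calendar (Table 8), footnote g sends the baseline biopsy to Section 9.1.2. Footnote h, for the post-cycle-2 biopsy, gives no handling reference.

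Section 13.5 assumes 16 patients with baseline and post-cycle-2 specimens for infiltrating lymphocytes and for PD-L1 and PD-L2 expression. It claims 80% power for a change of 0.65 SD, using a Wilcoxon signed rank test at two-sided 0.10.

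**The concern.** A site can follow a written protocol instruction exactly and still produce tissue that the written assay cannot use. Cores embedded in OCT and frozen are not paraffin sections, and the documents describe no frozen-section version of the PD-L1/PD-L2/PD-1 stain.

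Change in PD-L1 expression after radiation is part of a stated secondary objective (Section 1.3), and Section 9 plans immunohistochemistry on the sequential biopsy. That biopsy is optional and total accrual is at most 26 (Section 13.2), so there is little room to lose usable pairs.

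There is a second, conditional risk. If handling varied between sites, or between the two biopsies of one patient, and a laboratory adapted the stain to frozen material, the within-patient change would mix the effect of treatment with the effect of fixation.

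**Working it through.** **1. The two instructions side by side (fresh cores).**

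| Step | Section 9.1.2 | Appendix C, core route |
|---|---|---|
| First core | Formalin | OCT cassette |
| Second core | DMEM or RNAlater | OCT cassette |
| Further tissue | Alternates between the two routes | OCT cassettes |
| End product | Paraffin block and/or slides, plus tissue at -70 to -80C | Frozen OCT at -80C |
| Usable in Appendix F as written | Yes, the formalin cores | No |

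Both cannot be followed for the same core. Appendix C's effusion and fine-needle routes do yield a cell block, so the gap is confined to the core route.

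**2. Is there a rule of precedence?** Sections 5.2.1 and 5.3.1 name both sources and rank neither. Footnote g settles the matter for the baseline biopsy only. The post-cycle-2 biopsy, which has no substitute, has no specific pointer.

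**3. Which sample is lost?** At baseline, Section 5.2.1 collects archival tissue separately (a block, or 20 unstained slides). Section 9 accepts archival tissue or a baseline biopsy for enrollment and plans immune profiling on either. A frozen baseline core therefore need not cost a pair. This cover is not complete: Table 8 labels archival tissue optional, and the documents do not state outright that the blocks are paraffin. After cycle 2 there is no other source. If all of a patient's cores are frozen then, that patient has no post-treatment PD-L1/PD-L2 value from the Appendix F assay.

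**4. The plan's own figure.** Inputs from Section 13.5: n = 16 pairs, shift 0.65 SD, two-sided alpha 0.10.

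- Paired t, noncentral t with df = 15 and noncentrality 0.65 × √16 = 2.60: power 0.798.
- The same with n scaled by the Wilcoxon efficiency 3/π, so 16 × 3/π = 15.28: power 0.780.
- Normal approximation with that scaling: Φ(0.65 × √15.28 − 1.645) = Φ(0.896) = 0.815.
- Simulated exact Wilcoxon under normal differences: 0.770 (attained size 0.093).

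The stated 80% reproduces with the standard approximations and is not in dispute.

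**5. Illustration of lost pairs.** The number of pairs lost is an assumption, because the documents give no figure for it.

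| Pairs lost | Pairs left | Power, t with 3/π scaling | Power, exact Wilcoxon simulation |
|---|---|---|---|
| 0 | 16 | 0.780 | 0.770 |
| 1 | 15 | 0.754 | 0.747 |
| 2 | 14 | 0.725 | 0.712 |
| 4 | 12 | 0.659 | 0.645 |
| 6 | 10 | 0.580 | 0.546 |
| 8 | 8 | 0.487 | 0.441 |

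The first lost pair costs 2 to 3 points (0.780 − 0.754 = 0.026; 0.770 − 0.747 = 0.023).

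**The case against.** The best defense is that Appendix C is general guidance and that 9.1.2 is the trial-specific text. Appendix C is titled as guidelines and mentions breast biopsy and HER2 re-testing, which do not belong to this disease. Its frozen shipping address is still to be determined. Section 9.1.2 names laboratories and has the coordinator notified before a biopsy to arrange transfer. Footnote g cites 9.1.2 alone. A careful site might well follow 9.1.2 throughout. This stands as a limit on likelihood: nothing in the documents shows that any site would prefer Appendix C. It does not remove the conflict. The permissive wording in Appendix C concerns how much tissue to take, the OCT steps carry no such qualifier, and footnote h is silent.

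Several stronger readings are tempting, and the documents do not support them.

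- A reader might infer that patients would have no paraffin tissue at all. Archival blocks or slides may cover baseline.
- A reader might infer that every biopsy handled by Appendix C removes a pair. A frozen baseline core may be replaced by archival tissue, and a patient with both biopsies frozen loses one pair, not two.
- A reader might multiply cassettes by cores to count the tissue lost. The same step says the last cassette holds many small pieces, so no firm count follows. What matters is that none of the tissue is fixed.
- A reader might extend the paraffin requirement to the infiltration stains. Appendix F covers PD-L1, PD-L2 and PD-1. The CD3, CD4 and CD8 antibodies are listed in Appendix D without a tissue format, and Section 13.5 does not say how the lymphocyte percentage is measured.

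It is also fair that the biopsies are suggested or optional and that Section 13.5 treats the correlative analyses as mostly exploratory.

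**Conclusion.** The inconsistency is real and limited in scope. For fresh research cores, Section 9.1.2 and Appendix C cannot both be followed, no precedence is stated, and the Appendix C route gives tissue that the Appendix F PD-L1/PD-L2/PD-1 assay cannot take as written. The consequence is firm for a post-cycle-2 biopsy whose cores are all frozen: that patient leaves the 16 assumed PD-L1/PD-L2 pairs. At baseline it is conditional on archival tissue being unavailable or unsuitable.

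The size cannot be fixed from the documents. The power figures above show only what follows if a given number of pairs is lost, assuming roughly normal differences and a true change of 0.65 SD. Mixing of treatment and fixation effects is a possibility under uneven handling, not a demonstrated result of the plan. The primary endpoint, the 3-month PFS rate, is untouched. The point should be corrected because a core already frozen in OCT is lost to the written assay, whereas correcting the text is simple.

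**What to change.** 1. State in Section 9.1.2, and in the pointers in Sections 5.2.1 and 5.3.1, that 9.1.2 governs the allocation and handling of core biopsies.
2. Delete the OCT steps for cores in Appendix C, or replace them with a reference to 9.1.2.
3. Add the 9.1.2 reference to footnote h of Table 8, matching footnote g.
4. Require that the baseline and post-cycle-2 biopsies of one patient be handled in the same way.

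Keeping OCT for the optional cores would not be a clean alternative, because 9.1.2 already assigns those alternately to formalin and to DMEM/RNAlater. The cost is an amendment to wording and a note to sites. No extra tissue, visits or patients are needed.
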